10.6.1 Time Period for Collecting Pregnancy Information

The time period for collecting information on whether a pregnancy occurs is from the screening visit to 3 months after the last seviroptimut-L or placebo dosing. Information on pregnancies identified prior to randomization does not need to be reported to Polynoma LLC or designee.

10.6.2 Action to be Taken if Pregnancy Occurs

The investigator will collect pregnancy information on any female subject who becomes pregnant while participating in this study and for up to 3 months post the last seviroptimut-L or placebo dosing. Treatment and study-related procedures will be terminated, and the investigator will record pregnancy information on the appropriate form and submit it to Polynoma LLC (or designee) within 2 weeks of learning of a subject's pregnancy. The subject will also be followed to determine the outcome of the pregnancy. Information on the status of the mother and child will be forwarded to Polynoma LLC or designee. Generally, follow-up will be no longer than 6 to 8 weeks following the estimated delivery date. Any premature termination of the pregnancy will be reported.

While pregnancy itself is not considered to be an AE or SAE, any pregnancy complication or elective termination of a pregnancy for medical reasons will be recorded as an AE or SAE (see Section 10.7).

A spontaneous abortion is always considered to be an SAE and will be reported as such. Furthermore, any SAE occurring as a result of a post-study pregnancy and that is considered reasonably related to the investigational product by the investigator will be reported to Polynoma LLC or designee. While the investigator is not obligated to actively seek this information on former study participants, he or she may learn of an SAE through spontaneous reporting.

Subjects who become pregnant and discontinue study treatment will still be followed for overall survival.

10.7 Adverse Events (AE) and Serious Adverse Events (SAE)

The investigator is responsible for the detection and documentation of events meeting the criteria and definition of an AE or SAE, as provided in this protocol. When there is a safety evaluation during this study, the investigator or site staff will be responsible for detecting, documenting, and reporting AEs and SAEs, as detailed in both this section of the protocol and in the AE/SAE section of the study manual.

10.7.1 Definition of an AE

An adverse event can be any unfavorable and unintended sign (e.g., an abnormal laboratory finding), symptom, or disease temporally associated with the use of a drug, without any judgment about causality.

Only events that occur between randomization and 30 days following the completion of study drug administration for the subject will be reported as adverse events (i.e., 30 days after either the Month 24 dose or premature study drug termination). Events that occur between study of enrollment (signing of informed consent) and randomization will be documented as medical history.

For patients that roll over into the Open Label Extension Study, AEs that occurred >30 days from last dose of placebo will not be documented. However, AEs present on the day of but prior to the first dose of active drug will be documented as AEs.

10.7.2 Definition of an SAE

An adverse event or suspected adverse reaction is considered “serious” if, in the view of either the investigator or sponsor, it results in any of the following outcomes: death, a life-threatening adverse event, inpatient hospitalization or prolongation of existing hospitalization, a persistent or significant incapacity or substantial disruption of the ability to conduct normal life functions, or a congenital anomaly/birth defect. Important medical events that may not result in death, be life-threatening, or require hospitalization may be considered serious when, based upon appropriate medical judgment, they may jeopardize the patient or subject and may require medical or surgical intervention to prevent one of the outcomes listed in this definition. Examples of such medical events include allergic bronchospasm requiring intensive treatment in an emergency room or at home, blood dyscrasias or convulsions that do not result in inpatient hospitalization, or the development of drug dependency or drug abuse.

10.7.3 Disease-Related Events or Outcomes Not Qualifying as SAEs

An event that is part of the natural course of the disease under study (i.e., disease progression) should not be reported as an SAE. Progression of melanoma, basal and squamous cell skin cancers (non-melanoma skin cancer), or a new primary melanoma will be recorded in the clinical assessments in the CRF. Death due to disease progression is to be recorded in the eCRF and not as an SAE. However, if the progression of the underlying disease is greater than what would normally be expected for the subject, or if the investigator considers that there was a causal relationship between treatment with seviprotilimut-L or protocol design/procedures and the disease progression, then it must be reported as an SAE.

10.7.4 Clinical Laboratory Abnormalities and Other Abnormal Assessments as AEs and SAEs

Abnormal laboratory findings (e.g., clinical chemistry, hematology, urinalysis) or other abnormal assessments (e.g., ECGs or vital signs) that are judged by the investigator as **clinically significant** will be recorded as AEs and SAEs if they meet the definition of an AE or SAE. Clinically significant abnormal laboratory findings or other abnormal assessments that are detected during the study or are present at baseline and significantly worsen following the start

of the study will be reported as AEs or SAEs. However, clinically significant abnormal laboratory findings or other abnormal assessments that are associated with the disease being studied, unless judged by the investigator as more severe than expected for the subject's condition, or that are present or detected at the start of the study and do not worsen, will **not** be reported as AEs or SAEs.

The investigator will exercise his or her medical and scientific judgment in deciding whether an abnormal laboratory finding or other abnormal assessment is clinically significant.

10.7.5 Breaking of Study Blind for Medical Emergencies

As there is no known antidote for seviroptimut-L, knowledge of the treatment arm is unlikely to be of any benefit to patient care in the event of medical emergencies. Therefore, unblinding is discouraged. Patients should be treated with best supportive care in the event of medical emergencies thought to be caused by study drug.

If it is determined that knowledge of the treatment arm is absolutely necessary, the option of code break may be performed using the IVRS only by the Medical Monitor assigned to the study (the option to access the code break will not be made available to the investigator or his/her staff). After unblinding the subject will not receive any more seviroptimut-L or placebo dosing, but will continue to be followed according to the original schedule for disease recurrence and survival.

10.7.6 Reporting Adverse Events

The investigator is to record all directly observed AEs and all AEs spontaneously reported by the study subject on the Adverse Event CRF. In addition, each study subject will be questioned about AEs.

Each AE should be described in detail on the Adverse Event CRF and SAEs on a Serious Adverse Event form and include the following information: start and stop dates, CTCAE grading, relationship to study medication, action taken, and outcome.

The investigator will also assess the possible relationship between the AE and the study medication as well as any concomitant medications according to the following criteria (WHO definitions):

- Probable: A clinical event - including laboratory test abnormality - with a reasonable time sequence to administration of the drug, unlikely to be attributed to concurrent disease or other drugs or chemicals, and that follows a clinically reasonable response on withdrawal (dechallenge). Rechallenge information is not required to fulfill this definition.
- Possible: A clinical event - including laboratory test abnormality - with a reasonable time sequence to administration of the drug, but that could also be explained by concurrent disease or other drugs or chemicals. Information on drug withdrawal may be lacking or unclear.

- **Unlikely:** A clinical event - including laboratory test abnormality - with a temporal relationship to drug administration that makes a causal relationship improbable, and in which other drugs, chemicals, or underlying disease provide plausible explanations. If the relationship is judged unlikely, an explanation for this decision should be made.

10.7.7 Prompt Reporting of SAEs to Polynoma LLC or Designee

All SAEs, whether or not considered related to the investigational drug, must be reported within 24 hours through electronic data capture system. The initial report will require a brief narrative of the symptoms, course, and treatment of the event. The Medical Monitor will review the information provided, and the investigator will be contacted as needed to obtain additional information on the event, and to determine whether the event requires expedited reporting per regulatory requirements. The sponsor will promptly report to the FDA and other applicable regulatory agencies SAEs which are both unexpected and suspected to be related to the study drug, in accordance with Title 21 of the Code of Federal Regulations (CFR), Part 312.32 (21 CFR 312.32) and local regulatory requirements. The investigator should also comply with any applicable requirements related to the reporting of SAEs to the IRB/IEC.

Any SAE occurring while on study shall be reported for the period from randomization through 30 days post discontinuation of the active treatment portion of the study or the last injection, whichever is longer.

The investigator will provide an SAE follow-up report to the sponsor. In this report, the investigator is to assess and record the SAE in detail, including the date and time of onset, description, intensity, duration, outcome, etiology, relationship to study drug, and action taken. Any SAEs that continue at the subject's last study visit must be followed until the event resolves or follow-up is agreed to be adequate by the investigator, Medical Monitor, and sponsor.

The investigator and the Medical Monitor will review each SAE report and evaluate the relationship of the SAE to study treatment and to underlying disease. Based on the investigator's and sponsor's assessment of the SAE, a decision will be made concerning the need for further action. The primary consideration governing further action is whether new findings affect the safety of subjects participating in the clinical study. If the discovery of a new SAE related to seviprotimut-L raises concern over the safety of continued administration of study drug to subjects, the sponsor will take immediate steps to notify the FDA and all investigators participating in clinical studies of seviprotimut-L.

Further action that may be required includes the following:

- Modification of the protocol
- Discontinuation or suspension of the study
- Modification of the existing consent form and informing current study participants of new findings
- Addition of any newly identified seviprotimut-L-related AEs to the list of expected AEs

11 STATISTICAL CONSIDERATIONS

The details of the statistical considerations and specific statistical analyses to be performed are provided in a separate Statistical Analysis Plan (SAP). This section of the protocol provides an overview of the statistical design of the study with a focus on justifying the size of the study.

11.1 Data Monitoring Committee

A Data Monitoring Committee (DMC) will monitor subject safety and assess analyses of efficacy measures. The DMC's role in efficacy monitoring role will be to make a recommendation regarding initiation of Part B, evaluation of interim analyses in Part B, and monitoring for threats to the validity of the planned analyses of Part B data. The criteria to be used by the DMC are specified in the SAP.

11.2 Part A Methods

The statistical goal in Part A is the assessment of vaccine biologic activity based on immunologic biomarkers. The signal of biologic activity will be based on measures of immune activity to the vaccine where signals of immune activity are putative evidence of ultimate clinical benefit.

The immunology data to be used in the statistical criterion for Part A come from two assessments: (1) IgG/IgM Western blot method, and (2) T-Cell Elispot method. Each method provides an immune response dichotomous outcome for each patient (0 = negative, 1 = positive). Both assays will be performed in triplicate, and be based on a comparison of a pre-vaccination baseline (T_0) to the post-vaccination Week 10 visit (T_{10w}). A subject will be regarded as having a positive immune response if either method (Western blot or Elispot) is positive. For the Western blot assay, a value of 1 (success) indicates the presence of an antibody reactive band in the follow-up assessments that was either absent in pre-vaccination serum or whose intensity was at least 25% greater than the corresponding band in the baseline serum. A value of 0 indicates all other outcomes, including missing or failed assessments.

Details for the Western blot and Elispot assay procedures and analysis are included in the Endpoint Charter and Statistical Analysis Plan, respectively.

Overall success is defined as evidence that frequency of a positive immune response (by Western blot OR Elispot) in seviprotimut-L dosing arms is 20 percentage points or higher than those in the placebo arm (e.g., Arm 0 has a 25% “positive” response rate and Arm 2 has a 45% “positive” response rate). Thus, the null hypothesis is that the proportion of success in the seviprotimut-L dose arm is the same as or lower than the proportion of successes in the placebo arm. The specific alternative for each endpoint is evidence that the seviprotimut-L dose arm proportion of successes is 20 points or more higher than that for Arm 0. The number of subjects required per arm is computed to be 33. This computation takes into account 2 arms and 2 endpoints, an attenuated type I error probability of 0.1 because this is not a regulatory endpoint, and 80% power.

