Biological activity of seviprotimut-L was measured by the percentage of subjects who generated an IgG or IgM response to antigens contained in the vaccine as measured by Western blot assay or the percentage of subjects who generated a T-cell response as measured by Elispot assay. The analyses summarized here focused on Western blot results due to issues regarding specimen holding time and artifacts for the Elispot assays. A Western blot result was considered positive (showing an increased immune response) if a $\geq 25\%$ increase in the intensity of a band or bands at Week 10 vs Week 0 or a new/additional band at Week 10 was observed. The prespecified endpoint was that $\geq 20\%$ of patients in a treatment arm (40 µg or 100 µg) would show an increase in immune response compared to the placebo arm. Western blot data were available for 134 subjects (43 treated with 40 µg, 44 treated with 100 µg, and 47 treated with placebo). The analysis of the data using the prespecified dichotomous success criterion (each subject's response counted as positive or negative) showed that there was not an obvious difference between placebo and either the 40 µg or 100 µg arm, i.e., placebo induced an immune response at Week 10 vs Week 0 in similar numbers (ratio) as did each active arm as determined by Western blot.

The protocol allowed for the assessment of all available data for evidence of immune response based upon exploratory analyses. The data available for analysis of Western blot results for each subject were the treatment arm, two specimen collections (Week 0 and Week 10, 3 replicates for each specimen), and molecular weight bands (categorized into intervals or “bins”). The data structure complexity together with high variability inherent in Western blot data necessitated the use of advanced statistical modeling to assess for the existence of a vaccine effect. Specifically, analysis of variance using Mixed Model Repeated Measures (MMRM) methodology was used to test for a vaccine effect. The MMRM model fit contains main effect terms for the factors listed above plus all two-way interactions between these main effects plus the three-way interaction of these main effects.

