5.0 STATISTICAL CONSIDERATIONS

5.1 Part A

The size of Part A (33 patients per arm) was computed based on having no greater than a one-sided 20% likelihood of a false positive conclusion for the immune response statistical criterion. See the subsequent section [6.8.1 “Part A Immunological Statistical Success”](#) for the statistical operating characteristics of the Part A statistical analysis.

Recruitment will continue in Part A until the analysis of Week 10 data has been completed on the first 99 randomized subjects. This will result in an “over enrollment” for Part A to avoid a discontinuation of recruitment and ensure a complete data set for Part A evaluation.

Patients assigned to the Placebo arm during Part A accrual will be offered the option of receiving 40 µg seviprotimut-L selected from Part A under an Open-Label Extension protocol. Patients assigned to the Part A active arms will remain on the dose assigned and be followed until the end of the study. All Part A patients will be separately tabulated and used in the assessment of safety. They may also be used in exploratory efficacy analyses, but will not be part of the primary or secondary Part B evaluations.

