6.8.2 Immunological Statistical Success

Immunological statistical success is defined as either one of Arm 1 or Arm 2 having a higher proportion of positive immune response (defined above) being significant at the one-sided 0.10 level of significance. A relaxed significance level is justified because a high false positive probability is acceptable for this immune response evaluation. Fisher's exact test is to be used to perform these two tests. The overall likelihood of a false positive conclusion for these two comparisons will not exceed 0.20 adjusting for two tests (0.10 = 0.20/2). The following table shows approximate critical values of the difference being tested for various values of probability of success in Arm 0:

| Arm 0 Success Probability | Critical Difference |
|--|---------------------|
| 0.10 | 0.155 |
| 0.15 | 0.170 |
| 0.20 | 0.175 |
| 0.25 | 0.185 |
| Critical difference = this value or greater will be significant at the one-sided 0.10 level. | |

If only one of the two comparisons (Arm 0 versus Arm 1 or Arm 0 versus Arm 2) meets the statistical criterion then the dose associated with this arm may become the candidate dose for Part B. If both arms meet the statistical criterion, then the candidate dose may be selected based on the relative size of the proportion difference.

The dose to be used in the initiation of Part B will be based on all aspects of the analysis of the data collected and available from Part A. The primary consideration will be the statistical criterion specified above. Failure to meet statistical criteria for either Arm 1 or Arm 2 will not automatically preclude the initiation of Part B, however. The DMC is chartered to make a recommendation regarding initiation of Part B based in part on toxicity of the vaccine treatment compared to current FDA-approved treatment for resected melanoma (see DMC Charter).

The seviprotimut-L dose selected for the initiation of Part B is 40 μ g.

The analysis of other immunological data will be open-ended with the goal of identifying any immunological changes associated with the initiation of vaccine therapy.

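### Part A: 33 per arm does not deliver the stated 80% power at 25% vs 45% under the SAP's Fisher rule (about 72% for either dose, 57% per dose), and the protocol leaves its 0.1 level undefined

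*Protocol*

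**What the plan says.** Protocol 11.2 sizes Part A for a 20-point gain in the proportion of immune responders over placebo. Its example is that "Arm 0 has a 25% “positive” response rate and Arm 2 has a 45% “positive” response rate". It then states that "The number of subjects required per arm is computed to be 33". Of the calculation behind this it says that "This computation takes into account 2 arms and 2 endpoints", together with "an attenuated type I error probability of 0.1 because this is not a regulatory endpoint, and 80% power". The hypothesis is one-sided, since "the null hypothesis is that the proportion of success in the seviprotimut-L dose arm is the same as or lower than the proportion" in the placebo arm. The section names no test. It does not say whether 0.1 is per comparison or overall, or whether 80% refers to one dose, to either dose, or to one or both assays.

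SAP 5.1 describes the same 33 per arm as sized on "no greater than a one-sided 20% likelihood of a false positive conclusion", and sends the reader to the Part A success section for the operating characteristics. That section, SAP 6.8.2, specifies Fisher's exact test at one-sided 0.10 for each dose against placebo. Success is declared if either dose passes, and the overall false-positive probability is bounded at 0.20 (0.20/2 = 0.10 per test). It tabulates approximate critical differences (0.185 at a 25% placebo rate) with the note "Critical difference = this value or greater will be significant at the one-sided 0.10 level". It gives no power.

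Protocol 1.3.1.1 reports that on the prespecified yes/no criterion "there was not an obvious difference between placebo and either the 40 µg or 100 µg arm". Western blot data were available for 47 placebo, 43 (40 µg) and 44 (100 µg) subjects.

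**The concern.** The SAP's own table raises the doubt. If an observed difference of 0.185 is needed for significance and the true difference is 0.20, a trial of 33 per arm passes only a little more than half the time for a given dose. That is hard to square with 80% power. The two documents also attach different error rates, 0.1 and 20%, to the same sample size without saying how they relate.

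What is at stake is how the Part A result is read. The prespecified dichotomous comparison did not separate the arms, and the dose choice then drew on an exploratory mixed model. The weight that the dichotomous result can bear depends on its power, so the stated power should be the one that the specified rule delivers.

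**Working it through.** **Inputs.** n = 33 per arm, 25% vs 45%, type I error 0.1, 80% power (Protocol 11.2). Fisher's exact test, one-sided 0.10 per dose, either dose succeeds, critical difference 0.185 (SAP 6.8.2). One-sided 20% (SAP 5.1). Assayed sizes 47/43/44 (Protocol 1.3.1.1).

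**1. Where 33 could come from.** The usual two-proportion formula is n = [z(α)·√(2p̄(1−p̄)) + z(power)·√(p0(1−p0)+p1(1−p1))]² / (p1−p0)². Here p̄ = 0.35, √(2 × 0.35 × 0.65) = 0.6745 and √(0.1875 + 0.2475) = 0.6595.

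- One-sided 0.20: (0.8416 × 0.6745 + 0.8416 × 0.6595)² / 0.04 = 31.5, so 32 per arm. Power at 33 is 81.1%. This reproduces the plan's figure within two subjects.
- One-sided 0.10: (1.2816 × 0.6745 + 0.8416 × 0.6595)² / 0.04 = 50.4, so 51 per arm. Power at 33 is 66.7%. This does not reproduce it.

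So 33 follows if the SAP's 20% is used unsplit for a single comparison with a normal approximation. SAP 6.8.2 instead splits the 20% over two doses and uses Fisher's test.

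**2. Hand check from the SAP's table.** The standard error of the difference is √[(0.25 × 0.75 + 0.45 × 0.55)/33] = √(0.435/33) = 0.1148. The chance that the observed difference reaches 0.185 is about Φ[(0.20 − 0.185)/0.1148] = Φ(0.131) = 55%.

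**3. Exact power of the specified rule at 33 per arm.** For each placebo count x, let y*(x) be the smallest active count with one-sided Fisher p ≤ 0.10. For example, x = 8 needs y = 14 (difference 0.182), and x = 9 needs y = 16 (difference 0.212). Let c(x) = P(Y ≥ y*(x)) with Y binomial (33, 0.45).

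- Per-dose power = Σ P(X = x)·c(x).
- Either-dose power, with the shared placebo arm and both doses at 45% = Σ P(X = x)·[1 − (1 − c(x))²].

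| Quantity (25% vs 45%, n = 33) | Exact value |
|---|---|
| Power for a given dose | 56.7% |
| At least one dose, both at 45% | 72.1% |
| At least one dose, only one at 45% | 57.3% |
| Actual size per test, all arms at 25% | 0.0605 |
| Actual overall size, all arms at 25% | 0.105 |

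For 80% power, the Fisher rule needs 59 per arm for a given dose, or about 40 per arm for at least one dose when both work.

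**4. Power at the assayed sizes (47 placebo, 43 and 44 active), same rule and rates.** 40 µg: 68.5%. 100 µg: 71.9%. At least one dose if both are at 45%: 85.0%.

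**5. The type I error.** SAP 6.8.2 gives 0.10 per test and at most 0.20 overall. If the protocol's 0.1 is per comparison, the documents agree. If it is overall, they do not, and each dose would be tested at 0.05, where Fisher power at 33 per arm is 41.8% per dose.

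**The case against.** The strongest reply is that 33 is not a slip and that the protocol never called the 80% per-dose power. It says that two arms and two endpoints were taken into account, and the SAP counts either dose as success, so the matching figure is 72%, not 57%. Several readings also reach about 80% at 33 per arm:

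- one-sided 0.20 per comparison with a normal approximation (81.1%);
- either dose with an uncorrected chi-square test at 0.10 (81.6%);
- either dose with Fisher's test at a 15% placebo rate (80.2%);
- one dose with either of two endpoints, each tested by Fisher at 0.10 and assumed independent (81.3%).

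Part of this stands. The 80% is undefined, either-dose power is the one that matches the success rule, and 33 has a plausible origin. A reader might infer that 33 is an outright arithmetic error; the documents do not support that. But each rescuing reading changes the level, the test or the placebo rate, or treats the assays as separate independent tests. The protocol merges the two assays into one responder outcome, and SAP 6.8.1 makes Western blot primary and Elispot secondary. None of these readings is the specified rule at the stated example.

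A reader might also infer that the two documents use conflicting type I errors. That is not shown: 0.1 per comparison and 0.20 overall are compatible, and with Fisher's conservatism the actual overall size at a common 25% rate is about 0.105. What is shown is that the protocol leaves its level undefined.

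Finally, a reader might infer that the unclear Part A result came from an underpowered comparison, or that the dose decision is undermined. The documents do not support that either. The comparison used more than 33 per arm, and under the either-dose rule its power was 85% if both doses had the 20-point effect. Nowhere do the documents invoke the 80% to interpret the result. Protocol 9.2 and SAP 6.8.2 both say that missing the criterion does not by itself preclude Part B.

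**Conclusion.** The point holds in limited form. For the protocol's own example, the rule that the SAP specifies gives 72% power for at least one dose if both are effective, and 57% for a given dose or if only one works. The shortfall from 80% is about 8 points on the more favourable definition and 23 on the other. The protocol's 0.1 needs a definition; it agrees with the SAP only if it is per comparison.

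These figures assume one dichotomous endpoint, 33 evaluable subjects in every arm, and true rates of 25% and 45%. They depend on the placebo rate: at 15% with a 20-point gain, either-dose power is 80.2%.

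The consequence is small. Part A is complete, the dose has been chosen, and SAP 2.1 and 5.2 keep Part A subjects out of the Part B primary analyses. At the assayed sizes, power remains below 80% for each dose singly but not for the either-dose rule when both work.

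**What to change.** In Protocol 11.2, replace the 80% with the power of the specified rule: at 33 per arm and 25% vs 45%, Fisher's exact test at one-sided 0.10 per dose gives about 72% for at least one dose if both are effective, and about 57% per dose. State that 0.1 is one-sided per comparison with an overall bound of 0.20, matching the SAP. SAP 6.8.2 can carry the same sentence, since SAP 5.1 refers the reader there for operating characteristics.

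Where the Part A dichotomous result is interpreted, give the power at the assayed sizes: about 68% for 40 µg, 72% for 100 µg, and 85% for at least one dose if both work. Put it beside the confidence intervals for the differences in rates, which SAP 6.0 already plans for binary endpoints.

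The cost is a few sentences and a less favourable stated power. No subjects are added, and nothing in Parts B1 or B2 changes.
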